#### **Benefits and Risks:**

There may be no potential benefits from participating in this study other than more frequent assessment and observation. It is not known which technique actually provide the more favorable outcomes but both techniques are commonly used in clinical practice. The usual risks of combined spinal epidural labor analgesia include but not limited to : headache, failure of the spinal or epidural, intravenous catheter insertion and the extremely rare risks of bleeding, infection, nerve damage, paralysis, hypotension, high spinal block and even death rarely. All these risks are explained by the anesthesiologist participating or providing anesthetic care as part of the risk of neuraxial block.

#### **Statistics and Data Analysis:**

Data will be presented as mean (SD) or median as appropriate. Pain VAS scores will be examined, following tests for normality, by repeated measures two-way ANOVA in most study designs. Incidence data will be analyzed by Chi-Square or Fishers Exact Test. In the case of subject drop out, both intent to treat and completed treatment analyses will be performed. Continuous data will be compared by unpaired t-test and ANOVA. Assuming a difference in success rate of 95% versus 85% between the two groups, a sample size of 160/group is required to achieve a power of 0.8 and an alpha of 0.05. An estimate of 175/ groups or 350 total evaluable subjects will be enrolled in this study.

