**Purpose:**

The purpose of this study is to document the success rate and outcomes of combined spinal epidural labor analgesia when saline or air is used to identify the epidural space during the combined spinal epidural labor analgesia. Additional objectives of this study are to quantify the any complications and pain relief and satisfaction assessed by pain scores via randomized visual and verbal analog scores.

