**Procedures and Methods:**

Demographic data including patient's age, height, weight, gestation, medications and history of previous epidurals or spinals will be recorded. Patients will be randomized into one of two treatment groups (Group Air or Group Saline) according to a table of random numbers. The patient will be placed in the sitting position and a midline approach will be used as in usual practice. Combined spinal epidural labor analgesia will be performed in the usual manner, with group Air using 3 mL of air and group Saline using 3mL of saline in the syringe for identifying the epidural space during the combined spinal epidural labor analgesia placement. After positive fluid return from the spinal needle, a standard of care acceptable usual dose of labor analgesic will be administered at the discretion of the anesthesiologist providing the care. Typically 10-20 mcg of fentanyl with or without bupivacaine 1-2.5mg will be administered. The patients and data interpreters will be blinded to the treatment group; however, the anesthesiologist performing the procedure will not be blinded. Standard of care monitoring data will be recorded as usual, and level of pain relief will be obtained via pain scores by visual and verbal pain scores.

**RANDOMIZATION AND TREATMENT:** Patients will be randomized to have the anesthesiologist using saline or air for identifying epidural space during placement of the combined spinal epidural labor analgesia using standard loss of resistance technique. The chance of using air or saline is each 50%. The patients, data interpreters and analyzers will be blinded as to which group the patient is assigned to.

**Confidentiality:** All information obtained while you are in this study, as well as related hospital records, will be made available to the research staff and other regulatory authorities including the Food and Drug Administration (FDA). All information will be treated in a confidential manner and although the results of this research project may be presented at meetings or in publications, you will only referred to by number and your identity will not be disclosed in those presentations.

**SAFETY MEASURES:** Standard monitoring will be applied in the labor room as in usual clinical practice at Forsyth Medical Center. Unless other untowards effects are observed from the techniques, no additional monitoring will not be instituted.

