**OUTCOME MEASURES:** The primary outcome measure will be the success or failure of the combined spinal epidural labor analgesia. Secondary outcome measures are any complication or side effects.

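### Pain VAS: the planned repeated-measures ANOVA names no arm effect and no rule for incomplete score series; a mixed model on all available scores with one pre-named contrast is a cheap improvement (minor).

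*Combined protocol and SAP*

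**What the plan says.** The Statistics and Data Analysis section gives pain its own method: "Pain VAS scores will be examined, following tests for normality, by repeated measures two-way ANOVA in most study designs". The closing phrase is generic and was not fitted to this trial. Two neighbouring sentences bear on it. For losses, the section says "In the case of subject drop out, both intent to treat and completed treatment analyses will be performed". For other continuous measures, it says "Continuous data will be compared by unpaired t-test and ANOVA".

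The Purpose section makes pain an additional objective: "pain relief and satisfaction assessed by pain scores via randomized visual and verbal analog scores". The outcome-measures paragraph names success or failure of the block as primary and then says "Secondary outcome measures are any complication or side effects"; pain is not listed there. Procedures and Methods says only that "level of pain relief will be obtained via pain scores by visual and verbal pain scores", with no number or times of assessment. Repeated scoring is implied by the choice of a repeated-measures method and by the remark under Benefits and Risks that "There may be no potential benefits from participating in this study other than more frequent assessment and observation".

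No section names the arm effect to be tested, a time point, a sphericity correction, or a rule for a woman with some scores missing.

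**The concern.** Three things are left open, and each can affect the pain result.

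- **Which effect.** A two-way repeated-measures ANOVA yields two arm tests: group (are the arms different on average over time?) and group-by-time (does the difference change over time?). They address different hypotheses and can disagree. If the choice is made after the data are seen, the nominal 0.05 no longer holds. The sentence on the t-test and ANOVA adds options and does not choose between them.
- **Incomplete series.** Intent to treat names a population. It does not say how an incomplete series enters this ANOVA, and a woman who misses one score is not necessarily a drop-out in the plan's sense. The classical fit needs every score from every woman, so some randomised women would be left out and their observed scores discarded.
- **Sphericity.** With three or more assessments, the group-by-time test relies on sphericity, and no correction is named.

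At stake is the credibility of one additional objective that is likely to be reported. The primary comparison is not at stake.

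**Working it through.** **1. The plan's own figure.** The inputs come from the statistics section: "Assuming a difference in success rate of 95% versus 85% between the two groups", power 0.8, alpha 0.05. Two-sided testing is assumed because sidedness is not stated.

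Uncorrected n = [1.960·√(2·0.90·0.10) + 0.842·√(0.95·0.05 + 0.85·0.15)]² / 0.10² = (0.832 + 0.352)² / 0.01 ≈ 140.1, rounded up to 141.

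Continuity-corrected n = (140.1/4)·[1 + √(1 + 4/(140.1·0.10))]² ≈ 159.5, rounded up to 160.

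The stated 160 per group is reproduced. Pain VAS does not enter it, so nothing below changes it. The plan gives no figure for the VAS analysis.

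**2. Reading both arm tests.** With no true difference and compound symmetry, the group test uses each woman's mean and the group-by-time test uses within-woman contrasts, so the two are independent. The chance that at least one is significant is 1 − 0.95² = 0.0975. Simulation with 175 per group and 2, 4 or 6 assessments gave 0.094–0.102, rising to 0.121 with 6 assessments when correlation decays over time (AR(1), 0.7). Group-by-time alone, uncorrected, with AR(1) 0.5–0.7, gave about 0.06 with 4 assessments and 0.06–0.08 with 6. With 2 assessments there is no sphericity issue.

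**3. Complete series.** The number of assessments T and the missing rate are not in the documents. Assume 5% missing, out of 350 women:

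- each affected woman is lost once and stays lost (monotone, 5% in total): 350·0.95 ≈ 332;
- scores missing independently: 350·0.95^T = 316, 300, 285, 271 and 257 for T = 2, 3, 4, 5 and 6.

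**4. What discarding scores costs.** Let scores be missing independently at 2–10%, with within-woman correlation 0.3–0.7. The variance of the time-averaged arm difference from complete series, relative to a mixed model on all scores, is then 1.07–1.50 for T = 4 and 1.12–1.86 for T = 6. In one simulated case (T = 6, correlation 0.5, true difference 0.30 SD, loss more likely after a high score, 73% of series complete), the complete-series estimate averaged 0.25 SD and the all-available estimate 0.30 SD. That case meets the mixed model's own assumption, because loss depends on an observed score. It is an illustration, not a prediction.

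**5. Power of the candidate contrasts.** Assumed: SD 2.5, correlation 0.5 (compound symmetry), a sustained 0.5-point difference, 175 per group, two-sided 0.05, no missing scores.

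- One stated time: SE = 2.5·√(2/175) = 0.267; 0.5/0.267 = 1.87; power = Φ(1.87 − 1.96) = 0.46.
- Group effect: SE = 2.5·√{[(1 + (T − 1)·0.5)/T]·(2/175)}. For T = 2 this is 0.231, giving 0.58; for T = 6 it is 0.204, giving 0.69.

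With complete, balanced data, the time-averaged contrast from the mixed model has the same SE as the ANOVA group effect, so naming it costs no power. A single-time contrast can cost power.

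**The case against.** **The plan does not prescribe a complete-case analysis.** A reader might infer that it does. The text names a repeated-measures ANOVA and promises an intent-to-treat analysis; dropping incomplete series is a property of the classical fit, not a rule in the plan. This stands. The point is that the plan is silent on how incomplete series are kept, and that the usual fit would not keep them.

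**Naming one effect would repair most of it.** Largely true. Keeping the ANOVA with one named effect and a sphericity correction settles the choice and the error rate, but not the incomplete series. A single-time contrast is also close to the unpaired t-test already listed. The mixed model adds to that only where scores are missing, or if a pre-block pain score is recorded, which Procedures and Methods does not list among the baseline data.

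**The ANOVA is often the stronger test.** Against a single-time contrast this stands for a sustained difference (0.46 against 0.58–0.69). For a difference present only early, group-by-time has power 0.42–0.47 at correlation 0.5, about equal to 0.46, and 0.66–0.70 at correlation 0.7. The case for change therefore does not rest on power.

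**Missing scores from failed blocks.** A reader might take the planning rates (15% against 5% failure), suppose half of failed blocks have incomplete series, and see the failure gap among completers fall from 10.0 to 5.5 points (0.15·0.5/0.925 = 8.1% against 0.05·0.5/0.975 = 2.6%). That is a gap in failure rates, the primary outcome, which is analysed separately as incidence data. It is not a bias in VAS and should not be quoted as one. Nor would a mixed model repair loss driven by unrecorded pain.

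**The schedule is the prior gap.** This stands: without assessment times, no repeated-measures model can be specified.

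**Conclusion.** The point holds as a minor, cheap improvement. The plan leaves open which arm effect answers the pain question and how women with incomplete scores are kept. Fitted classically, the ANOVA would not meet the intent-to-treat promise for VAS if any scores are missing.

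The firmest figure is the 0.0975 false-positive chance. It needs no SD or missing rate, but it does assume sphericity and a reader who accepts either test as the pain result. The counts of complete series, the variance ratios and the power figures all rest on assumed inputs. The amount of missing data, and so the gain from the mixed model, cannot be computed from the documents; with no missing scores, the gain is confined to fixing the contrast.

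The documents do not support a wider claim that the trial's main conclusion or sample size is compromised. No case is made here against the normality check as such.

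**What to change.** 1. Set the number and times of pain assessments, and say how scores after delivery or after further analgesia are to be counted in the analysis.
2. Analyse all available scores from all randomised women with a linear mixed model: arm, categorical time, arm-by-time, unstructured covariance. A pre-block score can be added as a covariate if its recording is planned.
3. Name one arm contrast in advance, either the time-averaged difference or the difference at one stated time. Report it with a 95% CI and treat other arm effects as descriptive. The time-averaged contrast suits an expected sustained difference; a single time is simple to interpret but may have less power.
4. State that the model assumes missingness is explained by the observed scores, and that women with no scores contribute nothing.

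The cost is a few lines of SAP text and slightly more programming. No extra patients are needed and the sample size does not change.

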## **Human Subject**

This study will be performed in the Sara Lee Women's Center at Forsyth Medical Center, which includes monitoring and resuscitation equipment and trained nursing support staff. All studies will be approved by the IRB and written informed consent obtained. The Project Investigators have all performed similar studies in patients. The purpose of the study and all risks will be discussed with each subject, and all questions will be answered prior to obtaining written informed consent. Risks to be discussed include discomfort with needle and catheter insertion, risk of postdural puncture headache and spinal needle insertion. The usual side effects and risks of spinal and combined spinal-epidural anesthesia apply. These include itching, nausea, hypotension, unilateral pain relief, small risk of spinal tap, headache, bleeding, infection, venous catheter, high block or inadequate block. All data acquired will remain confidential with no reference to individuals in publications.

## **Data Safety Monitoring Plan**

These monitoring will be performed with a data safety monitoring board ([name] and [name]., MD), who are not involved in the study. Data and adverse events will be reported to these individuals, and reviewed on a regular basis. Adverse events will also be reported to the IRB. Serious adverse events will be reported to all of these groups and the data safety monitoring individuals within 24 hr and the trials halted until feedback is obtained from each.

